### 3.5 Analysis Plan

#### **Hypothesis 1.1 $PTSD_{dx}$ will discriminate PTSD patients from control subjects without PTSD;**

The primary evaluations will be based on computation of  $PTSD_{dx}$  and  $PTSD_{sev}$  markers similar to the approach used in preliminary studies. This will occur in multiple phases, all of which will randomly divide and analyze the full sample of 656 veterans into 3 groups of 219, 219, and 218 subjects, and in proportion to the presenting symptom/condition status of veterans, as follows:

Condition (Group)	Total N	Subsample		
		Sample 1	Sample 2	Sample 3
PTSD only (group A)	107	36	36	35
TBI only (group B)	126	42	42	42
PTSD & TBI (group C)	87	29	29	29
Depression only (group D)	80	26	27	27
Controls (no PTSD, TBI, depression) (group E)	256	86	85	85

To test our first hypothesis and in the first phase of analysis, we will use the specific  $PTSD_{dx}$  neuromarker previously identified in our preliminary study of 76 veterans, and evaluate it separately in all 3 subsamples. Analysis of covariance (ANCOVA) will be used to compare adjusted mean  $PTSD_{dx}$  scores between the PTSD only group (Group A) vs. planned contrasts with the remaining 4 groups. The a-priori-defined contrasts will consist of the following 5 comparisons: A vs. E, A vs. B/C/D combined, A vs. B, A vs. C, and A vs. D. Thus, for each subsample, there will be 5 planned comparisons, and hence a total of 15 comparisons. We expect the largest differences in mean  $PTSD_{dx}$  scores between PTSD only (group A) and controls (Group E), but nonetheless, also expect the PTSD only group to have higher mean  $PTSD_{dx}$  scores than Groups B, C, and D.

In these analyses, models will be adjusted for potential confounding variables (e.g. current use of sleep medications) identified by use of student *t*-tests (or Wilcoxon tests) for continuous variables and chi-square tests for categorical variables. Given the 5 planned comparisons for each subsample, a modified p-value of 0.01 will be used to define statistical significance. While arbitrary, “validation” of the previously identified  $PTSD_{dx}$  neuromarker will be based on statistical significance as follows: (i) all 3 comparisons of Group A vs. Group B at  $p<0.01$ , AND at least 9 of the 12 remaining comparisons at  $p<0.01$ .

In the second phase of this hypothesis, the approach used to identify the most promising  $PTSD_{dx}$  neuromarker described in Preliminary Studies will be applied to the much larger dataset of 656 veterans. For this analysis, Subsamples 1 and 2 will serve as training (development) samples, and Subsample 3 will serve as the validation sample. For subsample 1, ANCOVA will again be used to identify the 5 most promising  $PTSD_{dx}$  neuromarkers (based on corresponding *F* and *p*-values) rank ordered across the 5 planned comparisons described above. This process will be repeated for Subsample 2. From these results, the most promising  $PTSD_{dx}$  neuromarker will be selected based on the lowest aggregate rank scores across both subsamples and across all 5 planned comparisons. Once this  $PTSD_{dx}$  neuromarker is identified, it will be formally tested using the 5 defined planned comparisons within Subsample 3, and again using a *p*-value of  $<0.01$  to define statistical significance. In aggregate, these analyses will determine whether the originally identified  $PTSD_{dx}$  neuromarker can discriminate between veterans with and without PTSD, and whether a potentially

more promising  $PTSD_{dx}$  neuromarker is identified.

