## **2.2 Preliminary Studies**

In preliminary studies on EEG acquired during sleep from Veterans with PTSD alone (n=38), TBI alone (n=30), PTSD and TBI (n=25), and an aged matched no PTSD or TBI control group (n=38), we have shown that a set of neuromarkers were highly sensitive/specific to the presence of PTSD, and highly sensitive to the severity of symptoms in PTSD group.

The PTSD neuromarkers of this project are built from combination of regional brain coherence markers (BCM). BCM computation is based on the levels of coherence and synchronicity between pairs of scalp EEG activity. These coherence values were computed for the entire sleep study using

5-second sliding windows that were overlapped by 1 second. The frequency band spanned from 0.2 Hz to 50 Hz with a resolution of 0.2 Hz. Vectors of BCM were constructed over each of the five stages of sleep study (Awake [W], Rapid Eye Movement [REM], non-REM [NREM] stages N1, N2, and N3). Our analysis showed that the markers computed in awake and stage N2 sleep were significantly different in PTSD than the control group and also produced the highest level of correlation with the PTSD symptom.

The following figure shows the excellent capability of the PTSD diagnostic Neuromarker ( $PTSD_{dx}$ ) and PTSD severity marker ( $PTSD_{sev}$ ) in differentiating Controls from PTSD, and in correlation with symptoms, respectively.

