### 3.2 Type of Study

This project consists of three type of studies:

Study 1. This is a retrospective study. At ENRM VA, the Neuromarker analyses will be applied to a large existing database (n=656) containing sleep EEG recordings along with health and functional outcome measures, from Veterans with PTSD only (n=107), TBI only (n=126), both PTSD and TBI (n=87), depression only (n=80), and controls (no PTSD/TBI/Depression; n=256).

Study 2. This is a prospective pilot study at ENRM VA that will be conducted to evaluate potential improvement on the performance of the Neuromarkers using a dense array (up to 64 channels) EEG montage that covers all areas of the brain and with greater resolution, as compared to the original 6-channel EEG protocol. The sample will include up to 25 PTSD and control subjects.

Study 3. This is a prospective study conducted at ENRM VA on a single cohort of up to 55 Veterans with PTSD at multiple times during their ongoing clinical treatment for PTSD at the ENRM VA. Night time sleep EEG measures will be collected at pre-treatment, after first session of therapy, immediately after completion of therapy, and at 3-month post therapy. Measures of PTSD symptom severity, as well as measures of health and functional outcomes will be collected at the beginning and completion of therapy.

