De-identification and Data Transfer to ENRM VA: The PSG recordings in the data repository, comprised of electrophysiological measures (such as EEG, EOG, EMG) will be exported to a binary format and will be completely stripped of any identification marks and will be saved with coded filenames. A separate text file containing epoch by epoch (30 second duration) sleep stages will be also generated for each sleep study with no patient's identification inside the file nor as part of the filename. Other de-identified data includes a spreadsheet with demographic information and survey data from Table 1. The de-identified data will be transferred from Portland VA to ENRM VA via a shared network folder with limited access permission.

**Prospective Study I.** The retrospective study of the existing database is from clinical sleep studies where 6 EEG electrodes, covering the occipital, central, and frontal lobes of the two hemispheres, were used. This is because all sleep states can be scored by these limited number of electrodes. However, using these 6 EEGs limits the coherence analysis to general areas of the frontal, central, and occipital lobes and with no direct representation for other areas of the brain. The aim of this prospective study is to evaluate potential improvement on the performance of the Neuromarkers using a dense array (up to 64 channels) EEG montage that covers all areas of the scalp. In the control and PTSD subjects, we will perform sleep studies using a dense array EEG montage and will compare the performance of the Neuromarkers in distinguishing PTSD from non-PTSD groups.

This entails starting with the coherence analysis based on the six electrodes used in the preliminary study followed by evaluating the nominal improvement in discrimination ability (PTSD vs. absence of PTSD) with the use of extra channels. The control subjects will be recruited by

advertising in the Bedford VA common areas, and by distributing informational flyers via VA providers, Veteran organizations, and other Veteran networks (including Veteran Services Offices, Veteran Centers, CBOC's, and other programs). We may also place an advertisement on Craigslist. Eligible Veterans will be able to self-refer to be screened for the study. The PTSD group will be recruited from Veterans undergoing treatment of PTSD at ENRM VA before the start of their treatment (Veterans with PTSD recruitment described in Section 4.2.3).

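### Phase 1 tests the preliminary study's marker in all 656 repository records without checking whether the 76 Veterans behind that marker are among them

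*Combined protocol and SAP*

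**What the plan says.** Section 2.2 describes the preliminary work as sleep EEG from "Veterans with PTSD alone (n=38), TBI alone (n=30), PTSD and TBI (n=25), and an aged matched no PTSD or TBI control group (n=38"). The two 38s give the 76 cited in section 3.5. Section 2.2 does not name the source of the recordings.

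Section 3.2 describes the retrospective database as sleep EEG "from Veterans with PTSD only (n=107), TBI only (n=126), both PTSD and TBI (n=87), depression only (n=80), and controls" (n=256). Section 3.3 says these records come from the VA Portland sleep laboratory repository. Its criteria are referral to that laboratory and ability to consent; prior use of a record is not mentioned. The repository's director is a co-investigator.

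Section 3.5, Hypothesis 1.1, will "randomly divide and analyze the full sample of 656 veterans into 3 groups of 219, 219, and 218 subjects". Phase 1 takes the diagnostic "neuromarker previously identified in our preliminary study of 76 veterans, and evaluate it separately in all 3 subsamples". Each subsample has five planned comparisons of PTSD only (Group A) with other groups, and "a modified p-value of 0.01 will be used to define statistical significance". Validation requires all three A vs B (TBI only) results and at least 9 of the other 12 at that level.

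Hypothesis 1.2 applies a parallel approach to the severity marker, in the PTSD subjects of the same database.

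**The concern.** A marker chosen because it separated 38 PTSD-alone Veterans from 38 controls will look better in those Veterans than in new ones. If some of them are among the 656, Phase 1 is partly a test on development data. The design would not reveal this. The split is random over all records, so shared records would fall into all three subsamples, and agreement across the three would look like replication.

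What is at stake is the size of the reported group difference and how often single comparisons succeed. The same gap affects the severity marker under Hypothesis 1.2, which Hypothesis 3 then carries into the treatment study.

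**Working it through.** **1. The plan's own figures reproduce.** 107+126+87+80+256 = 656 and 219+219+218 = 656. 38+38 = 76, and all preliminary groups give 38+30+25+38 = 131. The threshold is 0.05/5 = 0.01. No power or effect size is stated for Hypothesis 1.1.

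**2. Evidence on overlap.**
- For: section 3.3 refers to "starting with the coherence analysis based on the six electrodes used in the preliminary study", and says "The retrospective study of the existing database is from clinical sleep studies where 6 EEG electrodes" were used. Both sets are Veterans' sleep EEG with PTSD, TBI and combined groups, and the repository director is on the team.
- Against: section 3.4 (item D-6) says the preliminary studies used PCL-M, whereas section 3.3 says all repository subjects completed surveys that include PCL-5.
- Not settled anywhere in the available text: the source of the preliminary recordings, or whether the two sets are disjoint.

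**3. Bounds.** Group A: 0 to 38/107 = 36%, or at most 38/3 ≈ 13 of 36 per subsample. Controls: at most 38/256 = 15% of Group E. The preliminary controls were free of PTSD and TBI but are not said to be free of depression, so some could sit in Group D instead.

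**4. Dilution formula.** Suppose selection adds a spurious difference d, split equally between the two groups, and a fraction f of the 76 is in the database. The A-E estimate then shifts by f × (38/107 + 38/256) × d/2 = f × 0.252 × d.

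**5. Weak true effect (assumed).** Simulation settings: true d = 0.3, best of 100 independent candidates chosen in 38 vs 38, SD 1, two-sided p<0.01, and all retained controls placed in Group E.

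| Overlap | A-E estimate | A vs E success per subsample |
|---|---|---|
| None | 0.30 SD | 13-14% |
| Half | about 0.37 SD | 23% |
| Full | about 0.44 SD | 34-35% |

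Check on the estimate: the selected marker's preliminary d averaged 0.91, an excess of 0.61. The formula gives 0.30 + 0.252×0.61 = 0.45 at full overlap, close to the simulated 0.44.

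Check on success: SE = √(1/36+1/86) = 0.1985 and P ≈ Φ(estimate/SE − 2.576). For 0.30, 0.37 and 0.44 this gives 14%, 24% and 36%.

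A vs B success per subsample rose from 10% to 20% at full overlap. All three A vs B tests succeeded in 0.1% of runs without overlap and 0.7% with full overlap.

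**6. No true effect.** With the best of 20, 100 or 500 null candidates and full overlap, A vs E reached p<0.01 in 2.1%, 3.0% and 4.5% of subsamples instead of 1%. All three A vs B tests succeeded in 0 of 3,000 runs in each setting. This agrees with arithmetic: at 100 candidates the A vs B rate was 1.8%, and 0.018³ ≈ 0.000006.

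**7. Cost of removal, worst case.** Without all 76, A falls to 107−38 = 69 and E to 256−38 = 218, or about 23 and 73 per subsample, and the total to 580. Power per subsample at an assumed d = 0.8, from Φ(0.8/SE − 2.576):
- A vs E: SE 0.199 → 0.239, power 93% → 78%.
- A vs B (36 vs 42 → 23 vs 42): SE 0.227 → 0.259, power 83% → 69%.
- If all 131 had to go (525 left, B = 96): A vs B power 64%.

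**The case against.** The strongest reply is that overlap is conjecture. Six electrodes are the standard clinical montage, so the match does not identify a source, and the PCL-M/PCL-5 difference is direct evidence against full overlap. This stands. A reader might infer that the validation does reuse development data, but the documents do not support that; they only fail to exclude it.

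A second reply is that the validation rule is demanding. This also stands. A reader might infer that a useless marker could be falsely validated. In the simulations none came through the A vs B requirement, and even a weak marker rarely did. The harm is to the estimate and to single comparisons.

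Third, it might be inferred that reported sensitivity and specificity would be biased. Aim 1 names them, but section 3.5 specifies only mean contrasts, so there is no planned analysis to which that claim attaches.

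Fourth, Phase 2 reselects the marker in Subsamples 1 and 2 and tests it in Subsample 3, and Hypothesis 2 evaluates it in newly recruited subjects. This protects Phase 2 but does nothing for Phase 1. It does mean that preliminary records need not be kept out of Subsample 3, unless preliminary results narrowed the candidates.

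**Conclusion.** The point holds as a gap in the plan, not as a demonstrated error. Phase 1 claims validation of a previously identified marker in a database that the documents do not show to be separate from the one that produced it. If there is no overlap, the effect is nil. If overlap is full, a true 0.3 SD difference would be reported as about 0.44 SD, and A vs E success per subsample would be about two and a half times as frequent.

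These sizes rest on assumptions that are not in the documents: the true effect, 100 independent candidates, two-sided tests, unit SD, and the degree and placement of overlap. Given the PCL evidence, the full-overlap figures are an upper bound under those assumptions, not an expectation. The change is worth making because it is cheap and because the check is easiest before identifiers are stripped.

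**What to change.** State in section 2.2 where the preliminary recordings came from. Before the de-identified transfer described in section 3.3, have the repository flag any record used in the preliminary study: the 76, and any of the other 30+25 = 55 that were used in developing the markers.

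Exclude flagged records from Phase 1 before the random split, and from the matching test of the previously identified severity marker under Hypothesis 1.2. Report the number removed, restate the subsample table, and give the all-records result as a sensitivity analysis. Phase 2, including Subsample 3, can keep them unless preliminary results narrowed the candidate markers; the plan should say which applies.

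The certain cost is one ID cross-check. If there is no overlap, a sentence saying so settles the matter. If there is, precision falls, at worst by the amounts in the last step of the working.

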### **1.0 Objective and Specific Aims:**

This project evaluates novel PTSD biomarkers which are based on measures of coherent activity among the regions of cerebral cortex during sleep. In preliminary studies on EEG acquired during sleep from Veterans with PTSD alone as well as other co-morbidities, we have shown that the neuromarkers were highly sensitive/specific to the presence of PTSD, and highly sensitive to the severity of symptoms in PTSD group.

The overall goal of this project is to further validate these novel neurophysiology markers in retrospective and prospective studies. The Overall hypothesis to be studied is as follows:

**Specific Aim 1:** Formally establish the sensitivity/specificity of the novel PTSD neuromarkers by analyzing a large existing dataset

**Hypothesis 1.1:** Neuromarkers can distinguish PTSD from non-PTSD groups with clinically acceptable sensitivity and specificity.

**Hypothesis 1.2:** In PTSD group, Neuromarkers will strongly correlate with PTSD symptom severity and measures of functional outcome.

**Specific Aim 2:** Evaluate improvement on the performance of the neuromarkers using a dense array EEG montage [Prospective Study 1]

**Specific Aim 3:** Evaluate the sensitivity of Neuromarker to the improvements in PTSD symptoms

Hypothesis 2: Neuromarkers will strongly correlate with the improvement of PTSD symptoms

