For this analysis, the most promising  $PTSD_{dx}$  neuromarker identified in Hypothesis 1.1 (phase 2 development and validation analysis) will be prospectively evaluated in up to 25 PTSD and control subjects. First, a standardized effect size (mean difference / standard deviation) and corresponding 95% confidence interval will be calculated for the  $PTSD_{dx}$  neuromarker using the conventional 6- channel EEG approach. Then, using forward stepwise linear regression, extra EEG electrodes whose addition increases the model coefficient of determination ( $R^2$ ) by at least 1% will be included as candidate extra EEG channels. Once a final model is fit (with  $>6$  electrodes), the corresponding standardized effect size and 95% confidence interval will be calculated. Given the pilot nature and sample size for this analysis ( $n=25$ ), interpretation will not be based on formal statistical testing, but rather on the difference in the two effects sizes generated from the 6-channel EEG analysis vs. the  $>6$ -channel EEG analysis. Given that effect sizes can be interpreted as “small” (0.2), “medium” (0.5), or “large” ( $\geq 0.8$ ), we will use half of the width of adjacent categories (i.e. 0.15) to interpret meaningful improvement with the use of more than 6 EEG channels. For example, if the standardized effect size for the 6-channel EEG was 0.70, the  $>6$ -

channel EEG effect size would need to be  $\geq 0.85$  to indicate meaningful improvement and potential indication for a more complex EEG testing approach.

**Hypothesis 3:  $PTSD_{sev}$  will strongly correlate with the changes of PTSD symptoms and other measures of Quality of Health and Life as a result of psychotherapy.**

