## **4.0 Human Subjects**

### **4.1 General Characteristics**

The project has three groups of human subjects’ involvement:

1. A retrospective study, where the analyses will be applied to a large existing database of health-related and functional outcome measures, as well as sleep EEG recordings. Database contains sleep EEG recordings from Veterans with PTSD only (n=107), with TBI only (n=126), with both PTSD and TBI (n=87), with depression only (n=80), and controls (no PTSD/TBI/Depression; n=256. The inclusion of records from TBI and depression only groups is to provide training data for the biomarker to become maximally sensitive and specific to PTSD in the presence of co-morbidities such as depression and TBI.
2. Prospective study 1 with up to 25 PTSD and control PTSD (n=10) and control (n=10) where we will evaluate potential improvement on the performance of the biomarkers using a dense array (up to 64 channel) EEG montage. For each participant, we will perform 2 sets of sleep studies that will be at least one week apart.
3. Prospective study 2 in a cohort (n=60) of Veterans undergoing psychotherapy, where we will evaluate the sensitivity of biomarkers to the improvements in PTSD symptoms, and other functional and HRQoL measures, in response to psychotherapy. These participants will undergo sleep studies at four times of time (a) Within one week before initiation of their treatment protocol; (b) Within one week after their first therapy session; (c) at the conclusion of their treatment phase; and (d) About three months after their last therapy sessions

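### No Hypothesis 1.1 contrast sets the PTSD & TBI group against a non-PTSD group, so a marker that misses PTSD when TBI is present can be declared validated

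*Combined protocol and SAP*

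**What the plan says.** Section 1.0 states the hypothesis as "Neuromarkers can distinguish PTSD from non-PTSD groups with clinically acceptable sensitivity and specificity". Section 3.5 closes Hypothesis 1.1 by saying the analyses will show whether the original "neuromarker can discriminate between veterans with and without PTSD".

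The contrasts in section 3.5, repeated in each of three subsamples, are "5 comparisons: A vs. E, A vs. B/C/D combined, A vs. B, A vs. C, and A vs. D". The text adds that the authors "also expect the PTSD only group to have higher mean" scores than groups B, C and D. Phase 1 validation needs all three A vs B tests at p<0.01 and "at least 9 of the 12 remaining comparisons" at the same level; the three A vs C tests are among those 12.

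Phase 2 ranks candidates by F and p-values, takes the marker with the "lowest aggregate rank scores across both subsamples and across all 5 planned comparisons", and tests it on the same five contrasts in Subsample 3. Hypothesis 2 then takes this marker forward: the "neuromarker identified in Hypothesis 1.1 (phase 2 development and validation analysis) will be prospectively evaluated in up to 25 PTSD and control subjects".

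Section 4.1 says that the TBI-only and depression-only records are there to make the biomarker "maximally sensitive and specific to PTSD in the presence of co-morbidities such as depression and TBI".

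**The concern.** Every contrast has PTSD only (A) on one side. Group C also has PTSD, but it stands on the other side each time: alone in A vs C, and pooled with the non-PTSD groups B and D in A vs B/C/D. Nothing in Hypothesis 1.1 asks whether C scores above B, D or E. Hypothesis 1.2 looks at severity among PTSD subjects, which is a different question from detection.

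This goes beyond a missing test, because separating the two PTSD groups is rewarded. A marker that reads PTSD equally well with and without TBI wins A vs C only by chance, and its A vs B/C/D difference is diluted. A marker that fails when TBI is present gains on both. At stake are the Hypothesis 1.1 conclusion and the choice of the PTSD_dx marker used in Study 2.

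**Working it through.** **Inputs from section 3.5.** Subsample sizes are A 36/36/35, B 42/42/42, C 29/29/29, D 26/27/27 and E 86/85/85. These sum to 219, 219 and 218, and the group totals to 107, 126, 87, 80 and 256, as stated.

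**The plan's own figures.** 0.05/5 = 0.01; 5 × 3 = 15 comparisons; 15 − 3 = 12 remaining. All reproduce. No effect size or power is given for this hypothesis, so there is none to reproduce.

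**Share of group C.** PTSD cases: 107 + 87 = 194, and 87/194 = 45%. Pool B/C/D: 126 + 87 + 80 = 293, and 87/293 = 30%.

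**Effect on one marker.** Let d be the standardised PTSD difference, with B = D = E = 0. If C = A = d, then A − C = 0, so each A vs C test is won about 1% of the time. In Subsample 1 the B/C/D mean is 29d/97 = 0.30d, so A vs B/C/D shrinks to 0.70d. The 12 counted tests consist of 3 A vs C and 9 others. Such a marker must in effect win all 9 others, 3 of them diluted.

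**Phase 1 pass rates.** The tests share group A, so the rule was simulated. Assumptions: SD 1, no covariates, pooled error, B/C/D weighted by group size, two-sided p<0.01 (the plan does not state sidedness). Results are accurate to about one percentage point.

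| Mean in C | d=0.8 | d=1.0 | d=1.5 |
|---|---|---|---|
| Not raised | 51% | 89% | 100% |
| Half of A | 31% | 77% | 100% |
| Equal to A | 15% | 53% | 99% |
| 1.5 times A | 7% | 45% | 100% |

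With B, C and D weighted equally, C = A passes in 12/45/98% and not raised in C in 50/89/100%.

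**Implied sensitivity over all 194 cases** (equal-variance normal scores, cut at d/2). For C = A it is Φ(d/2) = 66/69/77%. For a marker not raised in C it is [107·Φ(d/2) + 87·(1 − Φ(d/2))]/194. At d=0.8 this is (107 × 0.655 + 87 × 0.345)/194 = 52%; at d=1.0 it is 52%, and at d=1.5 it is 53%. The marker that passes more often finds about half the cases.

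**Phase 2.** F and p-values carry no sign. As an illustration, two independent markers of equal d were compared on |t| over 5 contrasts × 2 training subsamples and rank-summed. A marker not raised in C is picked over C = A in 70/73/77%, with 12–13% ties. A marker with C = 1.5A is picked over C = A in 45/46/47%, and C = A is picked in 36–38%; the rest are ties. The ranking thus penalises a C mean close to A: strongly in favour of C far below A, mildly in favour of C above A.

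**The case against.** **The A vs C contrast is deliberate.** It is pre-specified with a stated direction, and the plan admits that its validation rule is arbitrary. That stands. But the documents give no reason why PTSD with TBI should score lower. Even if it does, nothing tests whether C exceeds non-PTSD.

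**The Hypothesis 1.1 heading in section 3.5 speaks of PTSD patients against controls without PTSD, which A vs E tests.** True for PTSD without TBI. Section 1.0 and the closing sentence of Hypothesis 1.1 claim more.

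**A vs C is not mandatory.** Correct: 9 of 12 can be met without it. A reader might infer that a marker equal in A and C cannot be validated; the rule does not say that, and by about d=1.5 such a marker passes almost always. The preliminary results are described as highly sensitive and specific, so effects may be large. At that size, however, a marker blind in C also passes.

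**Stronger readings that the documents do not support.**
- That Phase 2 always favours lower scores in C. The C = 1.5A comparison contradicts this.
- That the simulated contests give the chance of selecting a poor marker. The plan shortlists five candidates per subsample from a pool whose size and correlation are unknown.
- That section 4.1 explains why group C was included. Its sentence is about the TBI-only and depression-only records; it supports the aim only through its reference to co-morbidity.
- That the present marker is blind to PTSD with TBI. Nothing shows this.

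**Conclusion.** The point holds. The contrasts cannot support a conclusion about veterans with and without PTSD, because 45% of the PTSD cases are never tested against anyone without PTSD, and a difference between the two PTSD groups counts as success. This follows from the text and needs no assumed effect size.

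The pass rates are illustrative and rest on assumed d, SD 1, no covariates and two-sided tests. The penalty on a marker equal in A and C matters for moderate effects and is gone by about d=1.5. The failure to stop a marker blind in C persists at large effects.

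The consequence is limited to the Hypothesis 1.1 conclusion and the marker evaluated in Study 2, a pilot of up to 25 subjects without formal testing. Study 3 uses PTSD_sev and is not affected. This should be fixed before the retrospective data are analysed.

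**What to change.** In Phase 1, the Phase 2 ranking and the Subsample 3 test, replace the five contrasts with (A+C) vs (B+D+E), A vs E, A vs B, A vs D and C vs B, each at p<0.01. Count a difference only when the PTSD side is higher, rank on the signed statistic, and report A vs C descriptively. Keep the requirement of all three A vs B and at least 9 of the other 12.

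State that the conclusion about veterans with and without PTSD also requires evidence from C vs B; otherwise it is limited to PTSD without TBI. The condition could be C vs B significant in at least 2 of 3 subsamples. In Phase 1, where the marker is already fixed, it could instead be one full-sample test of 87 vs 126. The full-sample form does not suit Phase 2, because Subsamples 1 and 2 select that marker; there the evidence is C vs B in Subsample 3 (power 76/94/>99.9% for C = A, 18/30/70% for a half-raised marker).

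**Cost.** Data, number of tests and alpha are unchanged, but the success criterion of a main hypothesis is altered. Phase 1 pass rates at d=0.8/1.0/1.5:

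| Mean in C | New contrasts, no C condition | With 2 of 3 C vs B |
|---|---|---|
| Equal to A | about 53/89/100% | 49/88/100% |
| Half of A | 34/81/100% | 6/20/78% |
| Not raised | 13/52/99% | under 0.1% |

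Some condition specific to C is needed, as the last row shows. The 2-of-3 form is costly for a marker that detects PTSD with TBI but less strongly. The full-sample test softens this: the power of C vs B alone is about Φ(δ·√(87·126/213) − 2.576) with δ = d/2. At δ=0.4 this is Φ(0.29) = about 62%, and at δ=0.5 it is Φ(1.01) = 84%. Letting the condition govern only the scope of the conclusion also lowers the price. Which form to use is the sponsor's choice, but it should be fixed in advance.

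### Aim 1 promises sensitivity and specificity, but the Hypothesis 1.1 analysis judges the marker only by p<0.01 contrasts of adjusted means and plans neither figure

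*Combined protocol and SAP*

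**What the plan says.** Section 1.0 gives Aim 1 as: "Formally establish the sensitivity/specificity of the novel PTSD neuromarkers by analyzing a large existing dataset". Hypothesis 1.1 follows: "Neuromarkers can distinguish PTSD from non-PTSD groups with clinically acceptable sensitivity and specificity". Section 4.1 says the TBI-only and depression-only records are included for the "biomarker to become maximally sensitive and specific to PTSD in the presence of co-morbidities such as depression and TBI".

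Section 3.5 (Analysis Plan, Hypothesis 1.1) splits 656 records into three subsamples and compares ANCOVA-adjusted mean scores. The groups are A (PTSD only), B (TBI only), C (PTSD and TBI), D (depression only) and E (controls). The five contrasts in each subsample are "A vs. E, A vs. B/C/D combined, A vs. B, A vs. C, and A vs. D". In Phase 1, validation of the "neuromarker will be based on statistical significance as follows": all three A vs B tests at p<0.01, and "at least 9 of the 12 remaining comparisons at" p<0.01.

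In Phase 2 a new marker is chosen by ranks of F and p-values in Subsamples 1 and 2. Then "it will be formally tested using the 5 defined planned comparisons within Subsample 3", again at p<0.01, with no stated number of contrasts that must succeed. The section closes by saying that these analyses will show whether the original marker "can discriminate between veterans with and without PTSD".

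**The concern.** A difference in group means is not a measure of how well individuals are classified. With enough records, a marker whose score distributions overlap heavily will give small p-values. A validated result under this rule would show that means differ, and there would be no figure to set against the hypothesis in Section 1.0.

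The contrasts also do not divide the records by PTSD status. Every contrast uses PTSD-only as the reference. Group C, whose members have PTSD, is tested against A and is pooled with B and D on the comparison side. The rule is therefore a poor proxy for sensitivity to PTSD accompanied by TBI, which Section 4.1 gives good reason to want. At stake is whether the lead aim can be answered at all, and whether a marker could be called validated while missing close to half of the PTSD records.

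**Working it through.** **1. The plan's own figures.** They reproduce. Threshold: 0.05/5 = 0.01 (the overall 0.05 is assumed; it is not stated). Comparisons: 5 × 3 = 15. Subsample totals: 219, 219 and 218. Section 3.5 gives no sample-size, power or accuracy calculation for Hypothesis 1.1.

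**2. Search for a planned accuracy measure.** Neither phase of Hypothesis 1.1 has one. The diagnostic percentages in Section 3.4 belong to the PSQI. The standardized effect sizes under Hypothesis 2 serve the dense-array pilot only.

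**3. What a just-significant contrast implies.** Assumptions: two-sided test, no covariates, normal scores with equal SD, cut-point midway between means. Subsample 1 has df = 219 − 5 = 214, so t(0.995) = 2.599. The smallest significant standardized difference is d = 2.599 × √(1/n1 + 1/n2). Then AUC = Φ(d/√2), and sensitivity = specificity = Φ(d/2).

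- A vs E (36, 86): d = 0.52, AUC 0.64, 60%/60%
- A vs B (36, 42): d = 0.59, AUC 0.66, 62%/62%
- A vs D (36, 26): d = 0.67, AUC 0.68, 63%/63%

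For comparison, 80%/80% needs d = 2 × 0.842 = 1.68, and 90%/90% needs d = 2.56. These targets are illustrative, since the plan states none.

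**4. What passing the whole Phase 1 rule implies.** The rule was simulated with the Section 3.5 subsample sizes (A 36/36/35, B 42/42/42, C 29/29/29, D 26/27/27, E 86/85/85), pooled variance on N − 5 df and 200,000 runs per scenario. Group A lies d above B, D and E alike, and group C lies f × d above them. Pass-rate ranges reflect equal or size-weighted pooling of B, C and D.

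Formulas, with 107 + 87 = 194 PTSD and 126 + 80 + 256 = 462 non-PTSD records:
- sensitivity in A = specificity = Φ(d/2)
- sensitivity in C = Φ(fd − d/2)
- A+C sensitivity = (107 × sens A + 87 × sens C)/194
- AUC = (107 × Φ(d/√2) + 87 × Φ(fd/√2))/194

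At d = 1.0, specificity is Φ(0.5) = 69% throughout, with 462 × 0.309, or about 143, false positives.

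| Group C scores | Rule passes | A+C sensitivity | PTSD missed, of 194 | AUC |
|---|---|---|---|---|
| like non-PTSD (f = 0) | 89% | (107 × 0.691 + 87 × 0.309)/194 = 52% | about 93 | 0.64 |
| halfway (f = 0.5) | 75-77% | (107 × 0.691 + 87 × 0.500)/194 = 61% | about 77 | 0.71 |
| like A (f = 1) | 45-53% | 69% | about 60 | 0.76 |

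At this d, the better a marker detects PTSD with TBI, the less often it passes.

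**5. Limits of that penalty.** With C at A's level the rule passes 80-86% at d = 1.2, 96-98% at d = 1.4 and over 99% at d = 1.68. For strong markers the rule instead stops distinguishing. At d = 1.4, a marker that misses C passes 99.9% of the time with 53% A+C sensitivity, and one that detects C passes 96-98% with 76%.

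**6. Check with a larger gap to controls, as Section 3.5 expects.** A is set 0.9 above B, C and D and 1.2 above E, with the cut-point maximising sensitivity plus specificity. The rule passes 74.5% of the time, with A+C sensitivity 57% and specificity 68%.

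**The case against.** The heading in Section 3.5 restates the hypothesis as discrimination only, the plan openly calls its rule arbitrary, and its closing claim is no stronger than that heading. This is fair as to candour, but Aim 1 still promises sensitivity and specificity, and differing means do not measure discrimination of individuals.

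The harshest scenario has group C scoring exactly like non-PTSD records, which nothing in the plan suggests. The plan does expect A to exceed C, and 9 of 12 lets all three A vs C tests fail. All of this stands. It limits the group C argument to an illustration, with the halfway and unequal-gap cases as milder versions. It supplies no accuracy figure.

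A cut-point may exist in the preliminary work, since the figure in Section 2.2 is not shown. This too stands and bears on the fix, but no analysis using such a cut-point is described.

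Finally, ROC figures could be computed later from the same records. They could, but a cut-point and acceptability limits chosen after seeing the data would be post hoc, which a formal validation is meant to avoid.

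Overall misclassification is not used here because it is uninformative at this prevalence: calling every record non-PTSD gives 194/656 = 29.6% error.

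**Conclusion.** The concern holds and should be fixed before analysis. The mismatch between Section 1.0 and Section 3.5 follows from the text alone and needs no simulation: the promised quantities are never estimated, no acceptable level is set, and no contrast compares PTSD with non-PTSD.

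The size is illustrative. It rests on normal equal-variance scores, two-sided tests, no covariates and assumed group differences. Under those assumptions, single contrasts reach significance at about 60-63% sensitivity and specificity, and the full rule can pass most of the time with A+C sensitivity between 52% and 61%. Whether such values are too weak is a judgement the plan leaves open by stating no minimum.

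**What to change.** Base the Hypothesis 1.1 conclusion on classification:

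- Report AUC, sensitivity and specificity with 95% confidence intervals for A+C versus B+D+E, plus sensitivity separately in A and C and specificity separately in B, D and E.
- For the original marker, use the preliminary-study cut-point if there is one. Otherwise derive it in Subsamples 1 and 2 and apply it in Subsample 3.
- For the Phase 2 marker, derive the cut-point in Subsamples 1 and 2 and lock it before that marker is evaluated in Subsample 3. Phase 1 will already have used Subsample 3 for the original marker.
- State minimum acceptable values before analysis and judge the estimates and their intervals against them. A criterion on the lower confidence limit is one option.
- State which database information defines PTSD; Section 3.3 lists both diagnosis history and PCL-5.
- Keep the ANCOVA contrasts as supportive; the confounder adjustment stays there.

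The cost is a few lines of SAP and a standard ROC analysis on existing records. Results may look less favourable than p-values, and precision is limited. With half-width 1.96 × √(0.8 × 0.2/n) at an assumed 80%, Subsample 3 gives about ±10 points for sensitivity (35 + 29 = 64 PTSD) and ±6 for specificity (42 + 27 + 85 = 154 non-PTSD). Sensitivity has about ±13 points in A alone (35) and ±15 in C alone (29). If the lower Wilson limit had to reach 70% (an assumed value), Subsample 3 would need at least 52/64 (81%) and 119/154 (77%) correct.

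With an external cut-point all 656 records could be used, for about ±5.6 and ±3.6 points. That requires the preliminary-study veterans to be outside the 656, which the document does not say.
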